8.3.1.12 Ankylosing Spondylitis spine MRI-activity (ASspiMRI-a) (Berlin modification) score

The Berlin modification of the ASspiMRI-a is a scoring system for assessing the sacroiliac joint with a concentration on short-tau-inversion recovery (STIR) sequences without other fat saturation techniques. This scoring method quantifies active changes in 23 vertebral units (VU) of the spine (from C2 to S1). A VU is defined as the region between 2 virtual lines through the middle of each vertebra. Active inflammation is scored by grading the degree of bone marrow edema from 0 to 3 in 1 dimension on one or more consecutive slices that represent the highest level of inflammation in a particular VU. Each VU score is called a subscore. These subscores are combined into a total spine ASspiMRI-a score in the Berlin modification (total score), which can range from 0 to 69.

The ASspiMRI-a (Berlin modification) score will only be assessed for study participants in the sacroiliac joint and spine MRI assessment sub-study who have both a Baseline and at least one post-Baseline MRI of the spine available.

The following imputation rules will be used for calculating the total spine ASspiMRI-a (Berlin modification) score:

- If all subscores are not readable or poor (N) at a visit, the total will be considered missing for that visit and the study participant will not be included in the analysis.
- If one or more but not all subscores are 'N', then subscores = 'N' will be considered as 0 when computing the total score.

Note that a reviewer may consider an assessment as not readable and assign a "N" value if the reviewer feels unable to evaluate a scan or an area of a scan at a specific location. This could be related to artifacts, image quality or something else.

If 2 independent readers are used, the analysis will use the average of the scores from the 2 independent reviewers.

In cases where disagreement between the two readers is large, a third adjudication reviewer will be required. The spine MRI adjudication trigger will occur when the difference in change scores (ie, change from Baseline to post-Baseline timepoint) of the two primary readers differs by ≥ 9 . If there are 3 readings, the analysis will use the average of the 2 closest change scores.

As already indicated in Section 3.3, the efficacy analyses for the MRI substudy will be performed using two sets of study participants based on the date of the Baseline MRI relative to the first study medication administration: 1) all eligible substudy participants with an MRI any

time prior to the first study medication administration, and 2) eligible substudy participants with MRI performed any time from 3 weeks prior to the first dose of study drug visit up to the first dose of study drug visit.

For the Week 16 visit, a time window of +/- 3 weeks before or after the scheduled visit may be considered appropriate for mapping MRI data to the given visit.

For the Week 52 visit, a time window of +/- 3 weeks before or after the scheduled visit may be considered appropriate for mapping MRI data to the given visit.

Only study participants with non-missing Baseline and at least one post-Baseline image will be included in this analysis. Therefore, no MI will be performed. The analyses will be conducted on the observed cases.

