The Double-Blind Treatment Period ends after Week 16 assessments. At Week 16, study participants will transition from the double-blind, placebo-controlled treatment into the 36-week Maintenance Period. Study participants receiving placebo during the Double-Blind Treatment Period will be re-allocated to bimekizumab treatment at Week 16 after all study assessments have been completed.

From Week 20 onwards, all study participants will be eligible for nonbiologic rescue therapy.

[figure not shown]
Prior to the completion of the Maintenance Period, Investigators should discuss treatment options with the study participant. Study participants who are not withdrawn from IMP and who meet the eligibility criteria will be given the opportunity to enter an extension study to continue to receive bimekizumab.

Study participants discontinuing IMP during the Double-Blind Treatment Period or during the Maintenance Period will be encouraged to return for all scheduled visits through Week 52 and the SFU Visit, as applicable.

A schematic representation of the study design is presented in [Figure 2–1](#).

This document cannot be used to support any marketing authorization application and/or variations thereof.

Figure 2-1: Study design

Refer to the study clinical protocol for more detailed information on the study assessments and schedule of procedures.

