Unless stated otherwise, statistical tests of efficacy variables will be performed 2-sided and p-values will be rounded to 4 decimal places. P-values less than 0.0001 will be presented as “<0.0001” and p-values greater than 0.9999 will be presented as “>0.9999.” Statistical comparison will be performed at the 0.05 level of significance.

The SAS® outputs supportive of any inferential statistics that are part of the hierarchical testing procedure (ie, all inferential statistics associated with the endpoints in figure 4.1) will be provided as a separate PDF document in addition to TFLs. These outputs will be included in the ‘Documentation of Statistical Methods’ section of the clinical study report.

Unless specified differently in the SAP, the order of treatment groups to be presented in tables from left to right will be:

- Placebo
- Bimekizumab 160mg Q4W

Selected tables may include columns for:

- all study participants, regardless of study treatment
- all study participants on bimekizumab, regardless of whether they shifted from placebo after the Double-Blind Treatment Period or not
- study participants randomized on placebo who shifted to bimekizumab after the Double-Blind Treatment Period

The abbreviation for bimekizumab is BKZ and will be used in tables and listings headers. In the TFLs study participants on bimekizumab 160mg will be displayed as “BKZ 160mg Q4W”.

All study participants dosed with bimekizumab will be summarized in some TFLs in a treatment column labeled as “BKZ 160mg Q4W Total”.

For all TFLs not dedicated to the Double-Blind treatment period only, the Placebo-randomized study participants who shifted to bimekizumab after the Double-Blind Treatment Period will be summarized in a treatment column labeled as “Placebo / BKZ 160mg Q4W”.

Per protocol,

- visit windows of ± 3 days are permissible for all visits through Week 16 (included). The visit window is relative to the Baseline Visit.
- visit windows of ± 4 days are permissible for all visits after Week 16,
- for the SFU Visit, the visit should occur no more than 3 days prior to the scheduled visit date and within 7 days after the scheduled visit date.

Only data collected at the scheduled visit will be included in the analysis. The only deviations may concern PK data, unscheduled vendor data collected with a few days of delay, and MRI data (see below).

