All by-visit summaries will contain nominal (ie, scheduled) visits only. Unscheduled visits will not be mapped to scheduled visits except for some assessments that may occur within 3-day time window of a scheduled visit. In that case, the assessment will be mapped to the corresponding scheduled visit and will be used for the analysis. Where scheduled visit data is available no mapping will be done, but if scheduled visit data is not available while unscheduled visit data within the 3-day time window is available, the unscheduled visit data collected on a day nearest to the scheduled visit day will be mapped and used in the analysis. This will only occur for PK data (see Section 9.1) some vendor data (see Section 10.4.3) and MRI data (see Section 8.3.1.12).

Assessments collected at unscheduled visits will only be listed, except in the case of determining Baseline, treatment-emergent markedly abnormal (TEMA) criteria for laboratory and vital sign parameters. For analyses on TEMA laboratory and vital sign, all post-Baseline (scheduled and unscheduled) values will be summarized in table outputs.

For by-visit tables summarizing efficacy data, the SFU visit will not be included. By-visit tables summarizing safety data should however include the SFU visit.

A complete set of data listings containing all documented data and all derived data (eg, change from Baseline) will be generated.

Unless otherwise stated, listings will be sorted by treatment, study participant number within each treatment group (not randomization number), variable (if applicable) and visit (if applicable; including timing relative to dosing if applicable). For listings including nonrandomized study participants, the nonrandomized study participants will be shown first in the listing, ordered by study participant number. All listings will include repeat and unscheduled measurements; such measurements will appear in chronological order together with the scheduled visits, ie, a repeated measurement will appear directly after the visit and time relative to dosing for which the repeat measurement was performed. In all the listings dates will be presented in the format 'YYYY-MM-DD' and times will be presented in 24h clock format as 'hh:mm'.

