3.2.2.1.2 Study periods for efficacy data

The following study periods are defined for the classification of efficacy data by study period:

- **Screening Period:** Starts at the time of the informed consent date and ends prior to the day and time of the first IMP administration.
- **16-Week Double-Blind Treatment Period:** Starts on the day of the first IMP administration and ends the day of the Week 16 Visit or on the day of the ET Visit for study participants withdrawn from the study before Week 16 visit. If Week 16 Visit is missing or skipped, the DBTP will end on the day of the last visit before Week 16.

Efficacy assessments from the Week 16 Visit belong to the DBTP as they are conducted prior to the Week 16 IMP administration.

- **36-Week Maintenance Treatment Period:** Starts on the day after the Week 16 Visit and ends the day of Week 52 Visit. If the Week 16 Visit is missing, the MP will start the day after the date of the last visit before Week 16. For study participants withdrawn from the study after Week 16 but before Week 52, the MP will end at the ET Visit.

A study participant will be considered to have completed a study period if they complete the last planned study visit for that period.

It is possible for a study participant to discontinue the study after completing the Week 16 efficacy assessments, (and therefore after completing the DBTP), but prior to entering the MP the next day. Therefore, all study participants who discontinue at or after Week 16 and never start the MP will be counted as having discontinued in the overall period only.

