8.3.3 Additional statistical analysis of selected other efficacy variables

Although statistical testing is not planned for other efficacy variables per protocol, statistical testing and inferential statistics are of interest for selected endpoints. As these tests are not part of the multiplicity-controlled procedure, the associated p-values are considered nominal and should not be used for inference. Similarly as described in Section 8.2.3, statistical tests and calculation of inferential statistics will be performed for the following selected other efficacy endpoints:

- ASAS40 at Week 1, Week 2, Week 4, Week 8, Week 12
- ASAS40 in the TNF alpha inhibitor-naïve study participants at Week 1, Week 2, Week 4, Week 8, Week 12
- ASAS20 at Week 1, Week 2, Week 4, Week 8, Week 12
- PGADA at Week 1, Week 2, Week 4, Week 8, Week 12, Week 16
- Total spinal pain at Week 1, Week 2, Week 4, Week 8, Week 12, Week 16
- Nocturnal spinal pain at Week 1, Week 2, Week 4, Week 8, Week 12
- BASFI at Week 1, Week 2, Week 4, Week 8, Week 12
- Mean BASDAI Q5 and Q6 score at Week 1, Week 2, Week 4, Week 8, Week 12, Week 16
- BASDAI at Week 1, Week 2, Week 4, Week 8, Week 12,
- BASDAI50 at Week 1, Week 2, Week 4, Week 8, Week 12, Week 16
- CRP at Week 1, Week 2, Week 4, Week 8, Week 12, Week 16
- ASDAS-CRP at Week 16
- MASES at Week 16
- Enthesitis free state at Week 16
- TJC at Week 16
- SJC at Week 16
- FACIT-Fatigue at Week 16
- WPAI at Week 16
- ASspiMRI at Week 16
- SPARCC at Week 16

The same models as described in Section 8.2.3 will be run, and results will be presented in one single table together with the results for secondary endpoints.

In addition, the Week 16 results from the primary analysis for the primary endpoint ASAS40, and key secondary endpoints in the hierarchy (ASAS20, BASDAI, BASFI, nocturnal spinal pain) will also be included in this table.

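### The Week 16 MRI window admits placebo scans taken after the switch to bimekizumab, and no rule clearly excludes them

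*SAP*

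**What the plan says.** On mapping MRI data to visits, SAP Section 8.3.1.12 states: "For the Week 16 visit, a time window of +/- 3 weeks before or after the scheduled visit may be considered appropriate". The sentence concerns MRI data in general. Section 8.3.1.13 sets no window of its own for SPARCC, so the same window presumably serves both scores.

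Section 2.3 says that placebo participants "will be re-allocated to bimekizumab treatment at Week 16 after all study assessments have been completed". Section 3.2.2.1.2 explains why Week 16 efficacy data count as double-blind data: "Efficacy assessments from the Week 16 Visit belong to the DBTP as they are conducted prior to the Week 16 IMP administration". It then defines the Maintenance Period for efficacy: "Starts on the day after the Week 16 Visit and ends the day of Week 52 Visit".

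Section 3.7 analyses efficacy by randomized arm. Section 8.3.3 plans nominal tests that include "ASspiMRI at Week 16" and the matching SPARCC comparison. Both MRI scores are analysed as observed cases without imputation (Sections 8.3.1.12 and 8.3.1.13).

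Section 3.1 has a general rule for mapping unscheduled data to a visit where "unscheduled visit data within the 3-day time window is available". It lists MRI among the data concerned and refers the reader to Section 8.3.1.12.

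**The concern.** The part of the window after Week 16 overlaps with active treatment in the placebo arm. A placebo-randomized participant scanned two weeks after the Week 16 visit has normally had a bimekizumab dose, yet the scan may be labelled Week 16 and summarised under placebo. The SAP's stated reason for treating Week 16 efficacy data as placebo-controlled, that they precede the dose, then fails for that scan.

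Week 16 is the only MRI time point named in the SAP at which a placebo comparison is possible, because both arms are on bimekizumab by Week 52. The effect on MRI inflammation is a stated objective (Section 2.1.3). At stake is whether the Week 16 MRI contrast compares bimekizumab with placebo, or with a mixture of placebo and early bimekizumab.

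**Working it through.** **Dates.** Count Baseline as Day 0.
- Scheduled Week 16 visit: 16 × 7 = Day 112.
- MRI window: 112 − 21 = Day 91 to 112 + 21 = Day 133.
- Part after the nominal switch: 21 of 42 days, or half.
- At the upper limit a placebo-randomized participant has nominally had 21 days since the first bimekizumab dose, against 112 days of double-blind treatment (21/112 = 18.75%). Section 3.1 allows the visit itself to move by 3 days either way, so the gap may be 18 to 24 days.

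**Does another rule remove such a scan?**
- *Period definition (Section 3.2.2.1.2).* By date, a scan after the Week 16 visit falls in the Maintenance Period. By the mapping rule it may be Week 16 data. The SAP does not say which prevails.
- *Observed-case rule (Section 4.2.1.10).* It opens by confining the analysis to participants who remain on their randomized treatment. The exclusion it then specifies covers only data after treatment discontinuation. The planned switch is not a discontinuation, and Section 8.1.2 counts only permanent discontinuations as intercurrent events. Read literally, the opening sentence would also remove every switched placebo participant from the Week 52 MRI summaries, for which Section 8.3.1.12 sets a window.
- *Analysis arm (Section 3.7).* Efficacy follows randomization, so a late scan stays with placebo.

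Elsewhere the SAP does respect the dose. Its restricted Baseline MRI set runs from 3 weeks before the first dose up to that dose (Section 3.3). Week 16 vital signs are split at dosing (Section 10.4.1).

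**Size.** The SAP gives no sample size, SD, effect or power for the MRI endpoints, so there is no stated figure to reproduce. Let D be the true Week 16 difference in mean change, f the share of placebo Week 16 scans taken after the switch, and g the share of D those scans already show. The placebo mean moves by f×g×D toward the bimekizumab mean, so the expected contrast is D × (1 − f×g). This assumes that late-scanned participants otherwise resemble the rest and that the bimekizumab arm is unchanged.

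Both f and g are assumptions. The value g = 0.19 is 21/112 rounded, as if the effect built up linearly. The last column takes a contrast with an assumed 80% power undiluted (two-sided 0.05, same standard error): power = Φ[(1.960 + 0.842)(1 − f×g) − 1.960].

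| f | g | Contrast retained | Power from 80% |
|---|---|---|---|
| any | 0 | 100% | 80% |
| 0 | any | 100% | 80% |
| 10% | 0.19 | 98.1% | 78.5% |
| 10% | 0.5 | 95.0% | 75.9% |
| 25% | 0.19 | 95.3% | 76.1% |
| 25% | 0.5 | 87.5% | 68.8% |
| 50% | 0.19 | 90.5% | 71.8% |
| 50% | 0.5 | 75.0% | 55.6% |
| 50% | 1 | 50.0% | 28.8% |

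**The case against.** The strongest reply is that the design places the switch after the Week 16 assessments. If the MRI is one of them, a post-switch scan is a departure from schedule and may be rare. MRI scheduling belongs to the protocol, which is not at hand. This stands as a limit on f. It does not remove the concern, because the window exists to accept off-schedule scans and does so on both sides of the dose. Section 3.3 records that several Baseline scans were more than 3 weeks before dosing. Timing drift therefore occurred in this substudy, although this says nothing about how many Week 16 scans were late.

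Second, the observed-case wording may be meant to exclude switched participants. That intention is possible, but the exclusion actually specified does not achieve it, so the two sections still need to be reconciled.

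Third, the mapping sentence is permissive and does not require late scans to be used. That is true. It also means that the rule is not fixed and that two programmers could select different scans.

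A reader might also infer a direct contradiction between the 3-day rule in Section 3.1 and the 3-week window. The text does not support that. Section 3.1 sends MRI to Section 8.3.1.12, much as it sends PK data to Section 9.1, which has its own windows. This is loose wording that one clause would settle.

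Finally, these are substudy endpoints outside the hierarchy, with p-values that Section 8.3.3 calls nominal and not for inference. Bias toward zero would not create a false claim of benefit. Both remarks are fair, and they limit the importance of the point.

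**Conclusion.** The point holds as a gap in the mapping rule. The window can place post-switch scans in the placebo arm at Week 16, and no other rule clearly takes them out. The resulting bias in the ASspiMRI-a and SPARCC contrasts is toward zero, with relative size f×g, provided that bimekizumab affects MRI inflammation within about 3 weeks.

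A reader might infer that the contrast is in fact diluted, or by how much. The SAP supports neither. It gives no value for f or g, and the bias is zero if either is zero. Late scans in the bimekizumab arm, which may reach Week 19, could offset a little of it. Nor does the point reach the primary endpoint, the key secondary endpoints or the multiplicity control. What is certain is the window and the missing cut-off; the size is conditional.

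**What to change.** In Section 8.3.1.12, replace the permissive sentence with a fixed rule for both arms and both MRI scores. Map to Week 16 only scans from 3 weeks before the scheduled visit up to the earlier of (a) the first Maintenance Period dose and (b) 3 weeks after the scheduled visit. Limit (b) is needed because Section 3.2.2.1.1 provides for participants who miss the Week 16 dose and start maintenance dosing later. Without it, their window could extend beyond the present one. List later scans, or use them only in a sensitivity analysis.

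In Section 3.1, state that MRI follows Section 8.3.1.12 and not the 3-day window. The Week 52 window does not need this cut-off, since both arms are then on bimekizumab.

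The cost is SAP wording and the loss of some late scans from the main MRI analysis. How many cannot be known from the SAP. The loss is not made up by imputation, because the analysis uses observed cases. Where the first Maintenance Period dose comes before the +3-week limit, the rule sets f to zero and so removes this source of bias.

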8.3.1.13 Spondyloarthritis Research Consortium of Canada (SPARCC) sacroiliac joint (SIJ) MRI score

The SPARCC is a scoring system for assessing the sacroiliac joint lesions based on STIR sequence. Each SI joint is divided into 4 quadrants (upper iliac, lower iliac, upper sacral, and lower sacral). The presence of increased signal on STIR in each of these 4 quadrants is scored on a dichotomous basis, where 1 = increased signal and 0 = normal signal. Joints that include a lesion exhibiting intense signal are each given an additional score of 1 per slice that demonstrated this feature. Similarly, each joint that included a lesion demonstrating continuous increased signal of depth greater than or equal to 1cm from the articular surface is also given an additional score of 1. The maximum score for a single coronal slice is 12. The scoring is repeated in each of 6 consecutive coronal slices. The total sacroiliac joint SPARCC score can range from 0 to 72.

Like the ASspiMRI-a (Berlin modification) score, the SPARCC score is only derived for study participants participating in the MRI sub-study who have both a Baseline and at least one post-Baseline MRI. The two sets of participants to be analyzed based on the date of the Baseline MRI relative to the first study medication administration are as described in Section 3.3, and the rules for handling poor or not readable images defined in Section 8.3.1.12 also apply. If 2 independent readers are used, the analysis will use the average of the scores from the 2 independent reviewers.

In cases where disagreement between the two readers is large, a third adjudication reviewer will be required. The SIJ MRI adjudication trigger will occur when the difference in change scores (ie, change from Baseline to post-Baseline timepoint) of the two primary readers differs by ≥ 13 . If there are 3 readings, the analysis will use the average of the 2 closest change scores. Only study participants with non-missing Baseline and post-Baseline data are included in this analysis. Therefore, no MI will be performed. The analyses will be conducted on the observed cases.

8.3.2 Analyses of other efficacy endpoints

The efficacy analyses described in this section are not part of the multiplicity-controlled testing procedure described in Section 4.5. Other efficacy endpoints will be analyzed as summarized in Table 4-1.

For the binary variables, the following two estimand structures will be defined:

- Composite Estimand - NRI:

- Population = Study participants enrolled according to the protocol-specified inclusion/exclusion criteria and randomized to IMP
- Study participant-level outcome = The given variable and time point being summarized
- Intercurrent event handling = An intercurrent event is defined as discontinuation of study treatment prior to the time point being summarized. A positive clinical outcome is defined as achieving the given variable at the specified time point and not having an intercurrent event date prior to the time point of interest.
- Population-level summary measure = Unadjusted number and percent of responders
Any missing data that are not preceded by an intercurrent event will be imputed based on NRI as well as any data after an intercurrent event, as described for the primary and secondary binary efficacy endpoints.
- Modified Composite Estimand – MI:
 - Population = Study participants enrolled according to the protocol-specified inclusion/exclusion criteria and randomized to IMP
 - Study participant-level outcome = The given variable and time point being summarized
 - Intercurrent event handling = An intercurrent event is defined as discontinuation of study treatment due to AE or lack of efficacy, prior to the time point of interest. A composite strategy will be implemented in which a positive clinical outcome is defined as achieving the endpoint at the time point of interest and not discontinuing study treatment due to AE or lack of efficacy through the time point of interest.
 - Population-level summary measure = Mean proportion of responders and 95% confidence interval.

An intercurrent event will be acknowledged as an unfavorable outcome for this modified composite estimand in considering study participants with intercurrent events as ‘non-responders’ to the study treatment.

Missing data that are not preceded by an intercurrent event will be imputed by standard MI techniques. Refer to Section 4.2.1.4 for further details.

All binary other efficacy variables will also be summarized using OC approach as defined in Section 8.1.4.6.

For all these variables, the results based on the NRI will be combined with the ones obtained on OC and from the MI analysis in one single table.

In addition, a line plot by treatment group will be produced over time for some of the endpoints, that are part of the sequential testing procedure, based on NRI results, including the following binary variables: ASAS40 responder rate, ASAS40 responder rate in the TNF alpha inhibitor naïve study participants, ASAS20 responder rate, ASAS5/6 responder rate, ASAS-PR responder rate, and ASDAS-MI responder rate.

Continuous other efficacy variables that are components of the primary endpoint will be analyzed using the reference-based MI estimand and procedure described in Section 8.1.4.3.

For the continuous and categorical other efficacy variables (not including change from Baseline in WPAI-SHP, ASspiMRI-a (Berlin modification) score, and SPARCC score, and EQ-5D-3L Utility scores), the following estimand structure will be defined:

- Hypothetical Estimand (Section 4.2.1.7) – MI:
 - Population = Study participants enrolled according to the protocol-specified inclusion/exclusion criteria and randomized to IMP
 - Study participant-level outcome = The given variable and time point being summarized
 - Intercurrent event handling = An intercurrent event is defined as discontinuation of study treatment prior to the time point being summarized. This estimand targets the treatment difference in a scenario where the intercurrent event does not occur, such that outcomes for study participants without an intercurrent event are as observed at the given time point, and outcomes for study participants with an intercurrent event are treated as though they had completed the randomized study treatment through the time point being summarized
 - Population-level summary measure = Unadjusted mean.

The same imputation strategy for handling missing data as the one used for the secondary continuous efficacy endpoints as described in Section 8.2.2 will be implemented. Missing data for ASDAS status endpoint will also be imputed using MI, and the imputation will be done on the components of ASDAS-CRP prior to calculating ASDAS-CRP and categorizing ASDAS status. The mean proportion of responders in the multiply imputed data sets (with the associated 95% CI based on SE) will be displayed for each ASDAS category.

In addition, a line plot by treatment group will be produced for some of the endpoints in the sequential testing hierarchy, displaying the mean change from Baseline for the following variables based on results obtained using MI: ASDAS-CRP, BASDAI, BASFI, Total Spinal Pain, Nocturnal Spinal Pain, PCS SF-36 and ASQoL. The plot will also be produced for ASDAS-CRP.

All other continuous and categorical variables will be summarized using descriptive statistics for Baseline, absolute values and change from Baseline at each visit (except for hs-CRP endpoint for which ratio to Baseline will be displayed). For other continuous variables whose value at Week 16 is part of the hierarchical testing procedure, descriptive statistics will also be provided using OC analysis. Categorical variables will be furthermore described using OC analysis.

The analyses on time to ASAS20/40 response will be restricted to the Double-Blind Treatment Period. Each time to ASAS20/40 response will be estimated and presented using the Kaplan-Meier product-limit method for each treatment group. The median time to response, including the 2-sided 95% CI, will be calculated for each treatment group. The Greenwood estimator will be used to estimate the variance of the survival. Comparisons of bimekizumab versus placebo will be analyzed using a log-rank test stratified by region and prior TNF α inhibitor exposure. The hazard ratio and 95% CI obtained from the Cox proportional hazards model as well as the p-value from the log-rank test will be displayed. The time points for calculating the number at risk is calculated in days but expressed in weeks, with each week corresponding to 7 days.

